### **3.1.2 Synovial Sarcoma (Treatment Group 2)**

- 3.1.2.1 Diagnosis of translocation associated sarcoma that generally expresses NY-ESO-1 (e.g., Synovial Sarcoma or Myxoid/Round Cell Liposarcoma). Tumor must have been reviewed by a bone and soft tissue pathologist. Patient must have metastatic or unresectable disease.
- 3.1.2.2 At least one prior line of chemotherapy
- 3.1.2.3 Age  $\geq$ 12 years. Patients  $\geq$ 18 years of age must be able and willing to provide informed consent. Patients under 18 years of age must have a parent or guardian willing and able to provide consent.
- 3.1.2.4 Eastern Cooperative Oncology Group (ECOG) performance status of 0, 1 or 2
- 3.1.2.5 Life expectancy greater than or equal to ( $>/=$ ) 12 weeks
- 3.1.2.6 Measurable disease, as defined by RECIST v1.1
- 3.1.2.7 Tumor safely accessible for biopsy
- 3.1.2.8 Adequate hematologic and end organ function
- 3.1.2.9 For female participants of childbearing potential and male participants with partners of childbearing potential, agreement (by participant and/or partner) to use highly effective form(s) of contraception as outlined in Section 5.7

### 3.2 Exclusion Criteria

#### 3.2.1 Mycosis Fungoides/Sézary Syndrome (Treatment Group 1)

- 3.2.1.1 Has disease that is suitable for local therapy administered with curative intent.
- 3.2.1.2 Patients who have had chemotherapy or targeted small molecule therapy within 4 weeks (6 weeks for nitrosoureas or mitomycin C) before entering the study.
- 3.2.1.3 Patients who have had an allogeneic stem cell transplant are excluded because such transplants disrupt the normal immune response to a very substantial degree. In addition, emerging data suggests exacerbation of lethal GVHD may occur in such patients when treated post allogeneic transplant with PD-1 blockade.
- 3.2.1.4 Has received prior therapy with an anti-PD-1, anti-PD-L1, or anti-PD-L2.
- 3.2.1.5 Patients who have received an investigational agent or have used an investigational device within 4 weeks of the first dose of study drug.
- 3.2.1.6 Has a history of a well-characterized and defined immune deficiency before the diagnosis of Mycosis Fungoides/Sézary Syndrome or is receiving systemic steroid therapy greater than 10mg/day of Prednisone or equivalent within 4 weeks or any other form of immunosuppressive therapy within 7 days before the first dose of trial treatment. The use of physiologic replacement doses of corticosteroids, along with topical, inhaled and local injection is discussed in [section 3.1.2](#).
- 3.2.1.7 Has had a prior monoclonal antibody within 4 weeks before study Day 1 or who has not recovered (i.e.,  $\leq$  Grade 1 or at baseline) from AEs due to agents administered more than 4 weeks earlier.

**Note:** The following will not be exclusionary:

- Patients may have any grade alopecia or lymphopenia and still participate if other inclusion/exclusion criteria are met. Patients may have grade 1 or 2 neuropathy at baseline and still participate if other inclusion/exclusion criteria are met.

- 3.2.1.8 Has a known additional malignancy that is progressing or requires active treatment. Exceptions include basal cell carcinoma of the skin, squamous cell carcinoma of the skin that has undergone potentially curative therapy, or in situ cervical cancer.
- 3.2.1.9 Patients with known brain metastases should be excluded from this clinical trial because of their poor prognosis and because they often develop progressive neurologic dysfunction that would confound the evaluation of neurologic and other adverse events.

Patients with carcinomatous meningitis should also be excluded.

Patients with previously treated brain metastases may participate provided they are stable (without evidence of progression by imaging using the identical imaging modality for each assessment, either magnetic resonance imaging (MRI) or computed tomography (CT) scan, for at least 4 weeks before the first dose of trial treatment and any neurologic symptoms have returned to baseline), have no evidence of new or

- enlarging brain metastases, and are not using steroids for at least 7 days before trial treatment.
- 3.2.1.10 History of allergic reactions attributed to compounds of similar chemical or biologic composition to MK-3475 (pembrolizumab) and Interferon-gamma. Patients who are hypersensitive to E. Coli are also excluded.
- 3.2.1.11 Has an active autoimmune disease that has required systemic treatment in the past 2 years (i.e., with use of disease modifying agents, corticosteroids, or immunosuppressive drugs). Replacement therapy (e.g., thyroxine, insulin, or physiologic corticosteroid replacement therapy for adrenal or pituitary insufficiency, etc.) is not considered a form of systemic treatment.
- 3.2.1.12 Has a history of (non-infectious) pneumonitis that required steroids or current pneumonitis.
- 3.2.1.13 Has a history or current evidence of any condition, therapy, or laboratory abnormality that might confound the results of the trial, interfere with the patient's participation for the full duration of the trial, or is not in the best interest of the patient to participate, in the opinion of the treating investigator.
- 3.2.1.14 Uncontrolled intercurrent illness including, but not limited to, ongoing or active infection, interstitial lung disease or active, non-infectious pneumonitis, congestive heart failure NYHA grade  $\geq 3$ , unstable angina pectoris, cardiac arrhythmia, or psychiatric illness/social situations that would limit compliance with study requirements.
- 3.2.1.15 Pregnant women are excluded from this study because MK-3475 (pembrolizumab) is an agent with the potential for teratogenic or abortifacient effects. Because there is an unknown but potential risk for adverse events in nursing infants secondary to treatment of the mother with MK-3475 (pembrolizumab), breastfeeding should be discontinued if the mother is treated with MK-3475 (pembrolizumab). These potential risks may also apply to Interferon-gamma. MK-3475 (pembrolizumab) and Interferon-gamma may have adverse effects on a fetus *in utero*. Furthermore, it is not known if MK-3475 (pembrolizumab) or Interferon-gamma have transient adverse effects on the composition of sperm. Patients are excluded from this study if pregnant or breastfeeding, or expecting to conceive or father children within the projected duration of the trial, starting with the screening visit through 120 days after the last dose of trial treatment.

See [Section 5.7](#) for information on contraception and pregnancy.

- 3.2.1.16 *Patients who are Human Immunodeficiency Virus (HIV) positive may participate IF they meet the following eligibility requirements:*
1. They must be stable on their anti-retroviral regimen, and they must be healthy from an HIV perspective.
  2. They must have a CD4 count of greater than 250 cells/mcL.
  3. They must not be receiving prophylactic therapy for an opportunistic infection.
  4. Must be on antiretroviral therapy and there must be minimal interactions or

overlapping toxicity of the antiretroviral therapy with the experimental cancer treatment.

5. HIV viral load must be <200 copies/ mm^3 by standard clinical assays.

3.2.1.17 Has known active hepatitis B (e.g., HBsAg reactive) or hepatitis C (e.g., HCV RNA [qualitative] is detected).

**Note:** The following will not be exclusionary:

1. A positive hepatitis B serology indicative of previous immunization (*i.e.*, HBsAb positive and HBcAb negative), or a fully resolved acute HBV infection
2. Patients with chronic HBV suppressed by appropriate antiretroviral therapy with activity against HBV, as outlined in DHHS guidelines
3. Positive HCV serology but no detectable HCV RNA, indicative of spontaneously cleared HCV infection
4. Patients who have been successfully treated for HCV as long as therapy for HCV has been completed

3.2.1.18 Has received a live vaccine within 30 days before the first dose of trial treatment. Examples of live vaccines include, but are not limited to, the following: measles, mumps, rubella, chicken pox, yellow fever, seasonal flu (some), H1N1 flu, rabies, BCG, and typhoid vaccine. Seasonal flu vaccines that do not contain live virus are permitted.

3.2.1.19 Has known psychiatric or substance abuse disorders that would interfere with cooperation with the requirements of the trial.

### 3.2.2 **Synovial Sarcoma (Treatment Group 2)**

- 3.2.2.1 Any approved or investigational anti-cancer therapy within 14 days prior to initiation of study treatment.
- Note: Prior treatment with anti-programmed death-1 (anti-PD-1) or anti-programmed death-ligand 1 (anti-PD-L1) therapeutic antibodies is allowed as is prior therapy with other immunotherapies.
- 3.2.2.2 Active or untreated central nervous system (CNS) metastases as determined by computed tomography (CT) or magnetic resonance imaging (MRI) evaluation during screening and prior radiographic assessments. Patients with prior brain metastases or CNS disease are permitted, but must have completed treatment and either (1) have no evidence of active CNS disease for at least 4 weeks prior to the first dose OR (2) have stable CNS lesions, or be at least 2 weeks past radiation or gamma-knife therapy. Patients with past CNS disease must also have a Screening head CT or MRI demonstrating stable disease compared to their most recent CNS evaluation.
- 3.2.2.3 Active therapy for malignancies other than sarcoma.
- 3.2.2.4 Pregnant and lactating women
- 3.2.2.5 New York Heart Association (NYHA) class 3 or 4 or clinically symptomatic cardiovascular disease
- 3.2.2.6 Severe infections requiring intravenous antibiotic treatment within 2 weeks prior to initiation of treatment
- 3.2.2.7 Major surgical procedure other than for diagnosis within 4 weeks prior to initiation of treatment
- 3.2.2.8 Active autoimmune disease requiring systemic treatment with steroids greater than 10 mg/day of prednisone or who have required steroids with a dose of 40 mg/day for the treatment of their autoimmune disease more than twice over the past year. Patients with an autoimmune disease who are on active therapy with a drug targeting TNF alpha.
- 3.2.2.9 Prior allogeneic stem cell or solid organ transplant
- 3.2.2.10 History of idiopathic pulmonary fibrosis, organizing pneumonia, drug-induced pneumonitis, idiopathic pneumonitis, or evidence of active pneumonitis on screening chest CT scan
- 3.2.2.11 Active tuberculosis
- 3.2.2.12 HIV on effective antiretroviral therapy will not be excluded.
- 3.2.2.13 Uncontrolled HBV infection, defined as plasma HBV DNA detectable by PCR
- Note: the following will NOT be exclusionary:
    - A positive hepatitis B serology indicative of previous immunization (i.e., HBsAb positive and HBcAb negative), or a fully resolved acute HBV infection
    - Patients with chronic HBV suppressed by appropriate antiretroviral therapy with activity against HBV, as outlined in DHHS guidelines
- 3.2.2.14 Uncontrolled HCV infection, defined as plasma HCV RNA detectable by PCR.
- Note: the following will NOT be exclusionary:

- Positive HCV serology but no detectable HCV RNA, indicative of spontaneously cleared HCV infection
- Patients who have been successfully treated for HCV as long as therapy for HCV has been completed

### **3.3 Inclusion of Women and Minorities**

Both men and women of all races and ethnic groups are eligible for this trial.

## **4. REGISTRATION PROCEDURES (TREATMENT GROUP 1 AND 2)**

### **4.1 Investigator and Research Associate Registration with CTEP**

#### **4.1.1 CTEP Registration Procedures**

Food and Drug Administration (FDA) regulations and National Cancer Institute (NCI) policy require all individuals contributing to NCI-sponsored trials to register and to renew their registration annually. To register, all individuals must obtain a Cancer Therapy Evaluation Program (CTEP) Identity and Access Management (IAM) account at <https://ctepcore.nci.nih.gov/iam>. In addition, persons with a registration type of Investigator (IVR), Non-Physician Investigator (NPIVR), or Associate Plus (AP) (*i.e.*, clinical site staff requiring write access to OPEN, Rave, or acting as a primary site contact) must complete their annual registration using CTEP's web-based Registration and Credential Repository (RCR) at <https://ctepcore.nci.nih.gov/rcr>.

RCR utilizes five person registration types.

- IVR – MD, DO, or international equivalent;
- NPIVR – advanced practice providers (e.g., NP or PA) or graduate level researchers (e.g., PhD);
- AP – clinical site staff (e.g., RN or CRA) with data entry access to CTSU applications (e.g., Roster Update Management System (RUMS), OPEN, Rave);
- Associate (A) – other clinical site staff involved in the conduct of NCI-sponsored trials; and
- Associate basic (AB) – individuals (e.g., pharmaceutical company employees) with limited access to NCI-supported systems.

RCR requires the following registration documents:

Documentation Required	IVR	NPIVR	AP	A	AB
FDA Form 1572	✓	✓			
Financial Disclosure Form	✓	✓	✓		
NCI Biosketch (education, training, employment, license, and certification)	✓	✓	✓		
GCP training	✓	✓	✓		
Agent Shipment Form (if applicable)	✓				
CV (optional)	✓	✓	✓		

An active CTEP-IAM user account and appropriate RCR registration is required to access all CTEP and Cancer Trials Support Unit (CTSU) websites and applications. In addition, IVRs and NPIVRs must list all clinical practice sites and Institutional Review Boards (IRBs) covering their practice sites on the FDA Form 1572 in RCR to allow the following:

- Addition to a site roster;
- Assign the treating, credit, consenting, or drug shipment (IVR only) tasks in OPEN;
- Act as the site-protocol Principal Investigator (PI) on the IRB approval; and
- Assign the Clinical Investigator (CI) role on the Delegation of Tasks Log (DLT).

In addition, all investigators act as the Site-Protocol PI, consenting/treating/drug shipment, or as the CI on the DTL must be rostered at the enrolling site with a participating organization (i.e., Alliance).

Additional information is located on the CTEP website at <https://ctep.cancer.gov/investigatorResources/default.htm>. For questions, please contact the **RCR Help Desk** by email at [[contact]](mailto:[contact]).

## 4.2 CTSU Registration Procedures

This study is supported by the NCI CTSU.

### 4.2.1 *IRB Approval*

For CTEP and Division of Cancer Prevention (DCP) studies open to the National Clinical Trials Network (NCTN) and NCI Community Oncology Research Program (NCORP) Research Bases after March 1, 2019, all U.S.-based sites must be members of the NCI Central Institutional Review Board (NCI CIRB). In addition, U.S.-based sites must accept the NCI CIRB review to activate new studies at the site after March 1, 2019. Local IRB review will continue to be accepted for studies that are not reviewed by the CIRB, or if the study was previously open at the site under the local IRB. International sites should continue to submit Research Ethics Board (REB) approval to the CTSU Regulatory Office following country-specific regulations.

Sites participating with the NCI CIRB must submit the Study Specific Worksheet for Local Context (SSW) to the CIRB using IRB Manager to indicate their intent to open the study locally.

The NCI CIRB's approval of the SSW is automatically communicated to the CTSU Regulatory Office, but sites are required to contact the CTSU Regulatory Office at [[contact]](mailto:[contact]) to establish site preferences for applying NCI CIRB approvals across their Signatory Network. Site preferences can be set at the network or protocol level. Questions about establishing site preferences can be addressed to the CTSU Regulatory Office by emailing the email address above or calling [name].

Sites using their local IRB or REB, must submit their approval to the CTSU Regulatory Office using the Regulatory Submission Portal located in the Regulatory section of the CTSU website. Acceptable documentation of local IRB/REB approval includes:

- Local IRB documentation;
- IRB-signed CTSU IRB Certification Form; and/or
- Protocol of Human Subjects Assurance Identification/IRB Certification/Declaration of Exemption Form.

In addition, the Site-Protocol Principal Investigator (PI) (i.e. the investigator on the IRB/REB approval) must meet the following criteria to complete processing of the IRB/REB approval record:

- Holds an Active CTEP status;
- Rostered at the site on the IRB/REB approval and on at least one participating roster;
- If using NCI CIRB, rostered on the NCI CIRB Signatory record;
- Includes the IRB number of the IRB providing approval in the Form FDA 1572 in the RCR profile; and
- Holds the appropriate CTEP registration type for the protocol.

#### ***4.2.2 Additional Requirements***

Additional requirements to obtain an approved site registration status include:

- An active Federal Wide Assurance (FWA) number;
- An active roster affiliation with the Lead Protocol Organization (LPO) or a Participating Organization (PO); and
- Compliance with all protocol-specific requirements (PSRs).

#### ***4.2.3 Downloading Site Registration Documents***

Download the site registration forms from the protocol-specific page located on the CTSU members' website. Permission to view and download this protocol and its supporting documents is restricted based on person and site roster assignment. To participate, the institution and its associated investigators and staff must be associated with the LPO or a PO on the protocol.

- Log on to the CTSU members' website (<https://www.ctsu.org>) using your CTEP-IAM username and password;
- Click on *Protocols* in the upper left of your screen
  - Enter the protocol number in the search field at the top of the protocol tree, or
  - Click on the By Lead Organization folder to expand, then select CITN, and protocol number CITN-13;
- Click on *Documents*, select *Site Registration*, and download and complete the forms provided.  
(Note: For sites under the CIRB initiative, IRB data will load automatically to the CTSU as described above.)

#### 4.2.4 Submitting Regulatory Documents

Submit required forms and documents to the CTSU Regulatory Office via the Regulatory Submission Portal on the CTSU website.

To access the Regulatory Submission Portal log on to the CTSU members' website → Regulatory → Regulatory Submission.

Institutions with patients waiting that are unable to use the Regulatory Submission Portal should alert the CTSU Regulatory Office immediately at [name] in order to receive further instruction and support.

#### 4.2.5 Checking Your Site's Registration Status

You can verify your site's registration status on the members' side of the CTSU website.

- Log on to the CTSU members' website;
- Click on *Regulatory* at the top of your screen;
- Click on *Site Registration*;
- Enter your 5-character CTEP Institution Code and click on Go

*Note:* The status shown only reflects institutional compliance with site registration requirements as outlined above.. It does not reflect compliance with protocol requirements for individuals participating on the protocol or the enrolling investigator's status with the NCI or their affiliated networks.

### 4.3 Patient Enrollment

#### 4.3.1 OPEN

The Oncology Patient Enrollment Network (OPEN) is a web-based registration system available on a 24/7 basis. OPEN is integrated with CTSU regulatory and roster data and with the Lead Protocol Organization (LPO) registration/randomization systems or Theradex Interactive Web Response System (IWRS) for retrieval of patient registration/randomization assignment. OPEN

will populate the patient enrollment data in NCI's clinical data management system, Medidata Rave.

Requirements for OPEN access:

- A valid CTEP-IAM account;
- To perform enrollments or request slot reservations: Be on a LPO roster, ETCTN Corresponding roster, or PO roster with the role of Registrar. Registrars must hold a minimum of an AP registration type;
- If a Delegation of Tasks Log (DTL) is required for the study, the registrar(s) must hold the OPEN Registrar task on the DTL for the site; and
- Have an approved site registration for a protocol prior to patient enrollment.

To assign an Investigator (IVR) or Non-Physician Investigator (NPIVR) as the treating, crediting, consenting, drug shipment (IVR only), or receiving investigator for a patient transfer in OPEN, the IVR or NPIVR must list the IRB number used on the site's IRB approval on their Form FDA 1572 in RCR. If a DTL is required for the study, the IVR or NPIVR must be assigned the appropriate OPEN-related tasks on the DTL.

Prior to accessing OPEN, site staff should verify the following:

- Patient has met all eligibility criteria within the protocol stated timeframes; and
- All patients have signed an appropriate consent form and HIPAA authorization form (if applicable).

**Note:** The OPEN system will provide the site with a printable confirmation of registration and treatment information. Please print this confirmation for your records.

Access OPEN at <https://open.ctsu.org> or from the OPEN link on the CTSU members' website. Further instructional information is in the OPEN section of the CTSU website at <https://www.ctsu.org> or <https://open.ctsu.org>. For any additional questions contact the CTSU Help Desk at [name] or [[contact]](mailto:[contact]).

Patient enrollment for this study will be facilitated using the Slot Reservation System in conjunction with the registration system in OPEN. Prior to discussing protocol entry with the patient, all site staff must use the CTSU OPEN Slot Reservation System to ensure that a slot on the protocol is available to the patient. Once a slot reservation confirmation is obtained, site staff may then proceed to enroll the patient to this study.

#### 4.4 General Guidelines

Following registration, patients should begin protocol treatment as soon as possible. Issues that would cause treatment delays should be discussed with the Principal Investigator. If a patient does not receive protocol therapy following registration, the patient's registration on the study

may be canceled. The Clinical Research Site (CRS) must notify the CITN Coordinating Center of cancellations as soon as possible.

## 5. TREATMENT PLAN

### 5.1 Agent Administration

[figure not shown]
Treatment will be administered on an outpatient basis. Reported AEs and potential risks are described in [Section 7](#). Appropriate dose modifications are described in [Section 6](#). No investigational or commercial agents or therapies other than those described below may be administered with the intent to treat the patient's malignancy.

#### 5.1.1 Mycosis Fungoides/Sézary Syndrome (Treatment Group 1)

##### *Treatment Plan*

- MK-3475 (pembrolizumab) will be administered at a dose of 200 mg every 3 weeks by IV infusion. No dose modification will be allowed.
- IFN-gamma will be initiated at 50 mcg/m^2 administered subcutaneously 3 times a week (e.g., M/W/F or T/Th/Sat).

Regimen Description (Treatment Group 1)					
Agent	Premedication; Precautions	Dose	Route	Schedule	Cycle Length
MK-3475 (pembrolizumab)	None	200 mg	Intravenous Refer to Section 8.1.1 for compatible infusion set materials including in-line filter.	Every 3 weeks (Day 1 of each cycle)	3 weeks
Interferon-gamma-1b	Antihistamines, analgesics, nonsteroidal anti-inflammatory drugs (NSAIDs), anti-depressants. Refer to Section 6.1.5	50 mcg/m  (Dose Varies, see below)	Subcutaneous	Three times weekly (e.g., M/W/F or T/Th/Sat)	Variable

The combination will be administered following the schema above:

- IFN-gamma lead-in treatment x 1 week => opportunity to obtain correlative biomarkers after IFN-gamma monotherapy for correlative studies
- Combination of MK-3475 (pembrolizumab) 200mg every 3 weeks and IFN-gamma 50 mcg/m^2 3 doses per week for 12 weeks
- Followed by MK-3475 (pembrolizumab) continued every 3 weeks up to 2 years. IFN-gamma boost (3 weeks) blocks every 2 cycles (6 weeks) of MK-3475 (pembrolizumab). IFN-gamma will be given 3 weeks on followed by 3 weeks off. If patients are experiencing intolerable toxicities and need additional time off, the investigator may increase time off in 1 week increments up to 3 weeks. A re-assessment of symptoms is made during this time period. The decision to increase time off is at the discretion of the investigator in consultation with the patient. If a patient is tolerating IFN-gamma well, IFN-gamma can be given continuously without break at the discretion of the investigator and in consultation with the patient starting at cycle 7. This option is intended for patients who experienced worsening of disease or associated symptoms during the cycles off of IFN-gamma, or in cases where the investigator believes the patient would otherwise benefit from continuous IFN-gamma therapy.
- Intra-patient dose increase for IFN-gamma: dose increases by 25 mcg/m^2 can be considered at each boost event if a CR cannot be confirmed at a global clinical assessment, to a max IFN-gamma dose of 100 mcg/m^2. If toxicity seen at higher IFN-gamma dose is deemed intolerable by the treating physician, the IFN-gamma dose can be reduced to the previously tolerable dose.

- The dose of IFN-gamma will be reduced to 25 mcg/m^2 for certain Gr 3 toxicities as outlined in [Section 6.1.4](#), and may be reduced at the investigator discretion to 25mcg/m^2 for constitutional symptoms as in [Section 5.1.1.2](#). If patients are experiencing intolerable toxicities, IFN-gamma may be held for up to a period of 3 weeks at the discretion of the investigator and in consultation with the patient. A re-assessment of symptoms is made during this time period, and treatment may be restarted at any point during the cycle. If such a hold occurs after cycle 5, treatment would recommence at the next planned cycle on IFN-gamma. For example, if IFN-gamma were held throughout cycle 8, the next IFN-gamma treatment would be at the start of cycle 10.

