## 6. DOSING DELAYS/DOSE MODIFICATIONS

### 6.1 Dose Modifications and Supportive Care Guidelines for Drug-Related Adverse Events (Treatment Group 1 and 2)

#### 6.1.1 MK-3475 (pembrolizumab) Dose Modifications

Adverse events (both nonserious and serious) associated with MK-3475 exposure may represent an immunologic etiology. These AEs may occur shortly after the first dose or several months after the last dose of treatment. MK-3475 must be withheld for drug-related toxicities and severe or life-threatening AEs as the table in [Section 6.1.3](#).

Dosing interruptions are permitted in the case of medical/surgical events or logistical reasons not related to study therapy (e.g., elective surgery, unrelated medical events, patient vacation, and/or holidays). Patients should be placed back on study therapy within 3 weeks of the scheduled interruption. The reason for interruption should be documented in the patient's study record.

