Toxicity	Hold treatment for Grade	Timing for Restarting Treatment	Treatment Discontinuation	CTCAE v5.0 Grade	Action / Supportive Care Guidelines
					
 
Diphenhydramine 50 mg PO (or equivalent dose of antihistamine).
 
Acetaminophen 500-1000 mg PO (or equivalent dose of antipyretic).
 

	3-4	Permanently discontinue	Permanently discontinue	3 f or 4 g	
Stop Infusion.
 
Additional appropriate medical therapy may include but is not limited to:
 
 
IV fluids
 
Antihistamines
 
NSAIDS
 
Acetaminophen
 
Narcotics
 
Oxygen
 
Pressors
 
Corticosteroids
 
Epinephrine
 
 
Increase monitoring of vital signs as medically indicated until the patient is deemed medically stable in the opinion of the investigator.
 
Hospitalization may be indicated.
 
Patient is permanently discontinued from further trial treatment administration.

Neutropenia, Thrombocytopenia	3	Hold MK-3475 and Interferon gamma until toxicity resolves to grade 0-1 and reduce Interferon gamma by 50% when restarting treatment	Toxicity >7 days or associated with bleeding requires discontinuation		
	4	Permanently discontinue	Permanently discontinue		
Hematologic AE other than neutropenia, thrombocytopenia or lymphopenia	3	Hold MK-3475 and Interferon gamma until toxicity resolves to Grade 0-1	Toxicity does not resolve within 12 weeks of last dose or inability to reduce corticosteroid to 10 mg or less of prednisone or equivalent per day within 12 weeks		

	Dose Modification Guidelines			Supportive Care Guidelines	
Toxicity	Hold treatment for Grade	Timing for Restarting Treatment	Treatment Discontinuation	CTCAE v5.0 Grade	Action / Supportive Care Guidelines
	4	Permanently discontinue	Permanently discontinue		
Skin-only Toxicity				2-4	Treat with topical corticosteroids (including high potency corticosteroids) and/or systemic corticosteroids. If systemic steroids are given, a steroid taper should start once symptoms improve to Grade 1 or less. For treatment group 1, if symptoms are consistent with a skin flare reaction, then management should follow the guidelines in section 5.9.
Drug-related neurologic sequelae including seizure, altered mental status or gait disturbance.	3-4	Permanently discontinue	Permanently discontinue		

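### For Group 1 patients escalated above 50 mcg/m², Sections 5.1.1 and 6.1.4 give different IFN-gamma restart doses after Grade 3 neutropenia or thrombocytopenia

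*Combined protocol and SAP*

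**What the plan says.** **Starting dose and escalation (5.1.1).** In Group 1, "IFN-gamma will be initiated at 50 mcg/m"², three times a week. Increases of 25 mcg/m² "can be considered at each boost event if a CR cannot be confirmed at a global clinical assessment, to a max IFN-gamma dose of 100" mcg/m². The dose at the time of a toxicity can therefore be 50, 75 or 100 mcg/m². It can also be 25 mcg/m² if the investigator has already lowered it for constitutional symptoms.

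**Reduction as written in 5.1.1.** "The dose of IFN-gamma will be reduced to 25 mcg/m"² "for certain Gr 3 toxicities as outlined in" Section 6.1.4. This is mandatory and names an absolute dose.

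**Reduction as written in 6.1.4.** For Grade 3 neutropenia or thrombocytopenia the table says: "Hold MK-3475 and Interferon gamma until toxicity resolves to grade 0-1 and reduce Interferon gamma by 50% when restarting treatment". This is also an instruction, but it scales with the current dose. The parent section is headed "Dose Modifications and Supportive Care Guidelines for Drug-Related Adverse Events (Treatment Group 1 and 2"), so the table applies to Group 1 as well as Group 2.

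**Optional step-down in 5.1.1.** If toxicity at a raised dose is judged intolerable by the treating physician, "the IFN-gamma dose can be reduced to the previously tolerable dose".

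**Group 2.** Notes in 5.1.2.2 and after the 6.1.4 table express the reduction both as 50 mcg/m² and as 50%. Group 1 has no equivalent note.

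**The concern.** Section 5.1.1 sends the reader to 6.1.4 for the Grade 3 toxicities that trigger a reduction. The row found there states a different kind of reduction from the one in 5.1.1. Both are written as requirements. In an escalated patient they cannot both be followed.

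Escalation is an intended part of the Group 1 regimen. Section 5.1.1 makes lack of a confirmed complete response the condition for considering an increase. Footnote a to 6.1.4 is firmer and says the dose will be increased in patients short of a complete response who are tolerating treatment. In the monotherapy trial described in Section 2.4.3, 1 of 24 patients had a complete response. Unless the combination does much better, most patients still on IFN-gamma at a boost would meet the response condition. Section 2.3.3 calls the cytopenias with IFN-gamma dose-dependent, so the triggering event may be more likely at the doses where the two texts part.

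Two things are at stake. Comparable patients could restart at different doses depending on which section a site consults. There would also be no single standard for judging a dosing deviation, in a trial where safety and tolerability is a secondary endpoint for Group 1.

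**Working it through.** The plan gives no figure to reproduce here. The check applies each written rule to every dose a Group 1 patient can be on.

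**Inputs.** Possible current doses *d*: 25 (lowered for constitutional symptoms), 50 (start), 75 and 100 mcg/m² (after one or two increases), all from 5.1.1.

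**Rules.**
- 5.1.1: new dose = 25, whatever *d* is.
- 6.1.4, Grade 3 neutropenia or thrombocytopenia: new dose = 0.5 × *d*.

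The two are equal only when 0.5 × *d* = 25, that is, *d* = 50.

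| Current dose (mcg/m²) | 5.1.1 | 6.1.4 | Difference | Ratio, larger to smaller |
|---|---|---|---|---|
| 25 | 25 | 12.5 | 12.5 | 2 |
| 50 | 25 | 25 | 0 | 1 |
| 75 | 25 | 37.5 | 12.5 | 1.5 |
| 100 | 25 | 50 | 25 | 2 |

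As a proportion of the current dose, the 5.1.1 rule is a cut of 1 − 25/75 = 67% at 75 mcg/m² and 1 − 25/100 = 75% at 100 mcg/m². The 6.1.4 rule is a 50% cut at every level.

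**Which Grade 3 events are covered.** In the 6.1.4 table the 50% instruction appears only in the neutropenia/thrombocytopenia row. The Grade 3 rows for other haematologic events and for all other drug-related toxicity call for a hold and state no IFN-gamma reduction. Grade 3 infusion reactions and neurologic events lead to permanent discontinuation. The neutropenia/thrombocytopenia row itself requires discontinuation if the toxicity lasts more than 7 days or is associated with bleeding. The conflict is therefore confined to Grade 3 cytopenias in that row after which a restart is allowed.

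**Does other text settle it?**
- 5.1.1.2 says only that doses are decreased as already described, and gives no number.
- Footnote a speaks of reductions for tolerability, most likely for constitutional symptoms. It does not tie the 50% to the starting dose or rank the two sections.
- The Group 2 notes apply to Group 2. There the starting dose is 100 mcg/m² and no escalation is described, so 50 mcg/m² and 50% are the same from that dose.

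**Timing against the week-10 safety review.** Increases occur at boost events and depend on a global assessment. The calendar places the first global assessment at cycle 6, weeks 16–18. That is after the pre-cycle-4 review at week 10.

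**The case against.** **Reconciling readings.** One could read 6.1.4 as listing the triggering toxicities and 5.1.1 as setting the Group 1 dose, so that the group-specific text governs. Or one could read the 50% as half of the starting dose, which gives 25 mcg/m² and removes the conflict. Both are possible intentions, but neither is written down. The 6.1.4 row states its own reduction under a heading that covers both groups, and it names no reference dose.

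**Scope.** A reader might infer that the sections conflict for Grade 3 toxicity in general. They do not, because only one table row states an IFN-gamma reduction. This limit stands.

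**Size.** A reader might count the optional step-down as a third Grade 3 rule. At 100 mcg/m² it gives 75, which would make a three-fold range (75/25). But that sentence is permissive, and its trigger is the physician's judgement of intolerability, not a toxicity grade. The firm spread between the two mandatory rules is two-fold. What remains is that the text does not say how the step-down relates to the Grade 3 rule when one event meets both triggers.

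**Data.** A reader might conclude that exposure and tolerability data after escalation cannot be interpreted. The documents do not support that. Optional increases, holds, continuous dosing from cycle 7 and investigator discretion already make IFN-gamma dosing variable by design. Doses as given can still be analysed. The inconsistency adds variation that depends on which section a site follows.

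**Safety.** Both agents are held until Grade 0–1 before restart. From 50 mcg/m² upward, either rule restarts at half the previous dose or less. That tempers the safety concern. It does not hold for a patient already at 25 mcg/m², where the 5.1.1 rule means no change.

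**Conclusion.** The contradiction is real and narrow. It concerns Group 1 patients who have a Grade 3 neutropenia or thrombocytopenia that permits a restart while on a dose other than 50 mcg/m². That mainly means patients escalated to 75 or 100 mcg/m², and also any already lowered to 25. The two mandatory instructions differ by a factor of 1.5 at 75 mcg/m² and by a factor of 2 at 100 and at 25 mcg/m².

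This rests on reading each sentence as written: a fixed dose in 5.1.1 and a percentage of the current dose in 6.1.4. The documents do not allow an estimate of how many patients would be affected.

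The response-rate design does not depend on this. Nor does the week-10 safety rule: it precedes any escalation, and it and the final safety criterion count patients with drug-related serious adverse events, with no dose level as an input. The consequence is inconsistent re-dosing after a Grade 3 cytopenia and no single reference for dosing compliance.

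**What to change.** Reconcile Section 5.1.1 with the Grade 3 neutropenia/thrombocytopenia row of Section 6.1.4, and with footnote a, into one Group 1 instruction. It should:

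- cover every permitted dose level (25, 50, 75 and 100 mcg/m²);
- make the cross-reference from 5.1.1 and the 6.1.4 row say the same thing;
- state how the Grade 3 instruction relates to the optional return to a previously tolerated dose.

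Which rule is right is a clinical decision for the sponsor, and this review takes no view on it. The cost is a protocol clarification. Sample size, decision thresholds and analyses do not change.
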